Appendix 3. Determination of Efficacy – Non-Hodgkin’s Lymphoma

Efficacy will be assessed using the International Working Group response criteria (Cheson Criteria Version 2007). Tumor responses are determined using information from objective measurements from CT scans, as well as clinical information including B-symptom evaluation, physical examination, ECOG performance status, assessment of liver and spleen, laboratory assessments such as bone marrow biopsies and/or aspirates, biochemical markers of disease activity (ie, LDH) and hematology results.

Tumor and clinical assessments will be performed as described in the Tumor Assessment flowchart. Treatment delays should not alter the schedule of tumor and clinical assessment evaluations and should continue at the frequency outlined in the flowchart.

For patients to be considered evaluable for efficacy, they must have completed at least 1 follow-up radiological tumor assessment post randomization, they must have received sufficient investigational product (at least one cycle of PF-05082566) and they must not have had any major protocol violations as determined by the sponsor.

Measurable/Abnormal Lesions

A nodal site of disease is considered measurable/abnormal if:

- Any nodal lesion can have a single diameter of >15 mm in the GTD, and the perpendicular dimension to the GTD must have a diameter >10 mm in order to be considered abnormal and measurable.
- Any nodal lesion can have >10 mm through ≤15 mm in the GTD, and the perpendicular dimension to the GTD must have a diameter >10 mm to be considered abnormal.

A nonnodal site of disease is considered measurable/abnormal if it measures ≥10 mm in 2 perpendicular dimensions.

Nonmeasurable Lesions

All non nodal sites of disease that that measure <10 mm in a single GTD are considered non measurable. Other sites of disease that are considered evaluable, but not measurable include pleural effusions, ascites and bone lesions.

Index Lesions

Up to 6 measurable/abnormal lesions should be selected as index lesions. Lesions can be selected as index lesions if they are clearly measurable in 2 perpendicular dimensions. Lesions cannot be selected as index lesions if they have been in an area of prior radiotherapy without evidence of progression. These lesions should be selected from disparate regions of the body as possible and should include mediastinal and retroperitoneal sites if these sites are involved. The greatest transverse diameter and the greatest perpendicular transverse diameter will be recorded for each index lesion. The product of these 2 dimensions will be recorded and the sum of the product diameters (SPD) of the index lesions will be the baseline value used in determining response.

Non-Index Lesions

All other lesions, either measurable or non measurable, are considered non index lesions. Multiple lesions may be grouped together as a non-index lesion (ie, multiple bony lesions in scapula). The status of the non index lesion will be recorded on the CRF.

Method of Measurement

- At a minimum, conventional CT or MRI should be performed with contiguous slices of 10 mm or less in thickness. Spiral CT should be performed by use of 8 mm or less contiguous reconstruction interval. The same method of measurement should be used throughout.
- CT scans with contrast should be performed for radiographic assessments. If a chest CT is not feasible with contrast, a non contrast CT should be performed. If CT abdomen/pelvis with contrast is not feasible, then an MRI of the abdomen/pelvis should be performed.
- Positron emission tomography (PET) scans should not be used for the determination of response, however, may be obtained if clinically indicated. Additionally, ultrasounds should not be used for purposes of measuring or evaluating disease in this study.

Clinical Assessments

In addition to radiographic tumor measurements, other clinical assessments should be obtained when evaluating disease. These include:

- Physical examination findings, evaluation presence, absence or any new lymph nodes. Additionally, an assessment of ECOG performance status will be obtained.
- Evaluation of B-symptoms.
- Bone marrow biopsies and/or aspirates.
- Evaluation of the liver and spleen.
- Biochemical markers of disease, including LDH.

Response Criteria

Evaluation of Index Lesions

Term	Definition
Complete Response	
Complete disappearance of all detectable clinical and radiographic evidence of disease.
 
All lymph nodes must have returned to normal size. If a lymph node GTD was ≥ 15 mm, it must have returned to < 15 mm. If the short axis was > 10 mm and the GTD was > 11 mm, it must have returned to ≤ 10 mm.
 
The spleen and/or liver, if enlarges prior to therapy on PE or CT, should no longer be palpable on PE and normal by imaging.

Partial Response	
$\geq 50\%$ decrease in the SPD of up to 6 index lesions.
 
No increase in size of other nodes, liver or spleen.

Stable Disease	Failure to attain a CR/PR or PD.
Progressive Disease/Relapsed Disease	$\geq 50\%$ increase in SPD of previously involved sites from nadir.
Unable to Evaluate	
Incomplete data (ie, missing scans or unreadable images).
 
Not all index lesions evaluated.
 
Index lesions not assessed.

Evaluation of Non-Index Lesions

Term	Definition
Complete Response	Complete disappearance of all non-index lesions.
Stable Disease/Incomplete Response	Persistence of one or more non-index lesion not qualifying for CR or PD.
Progressive Disease	
Any new nonnodal lesion.
 
Any new nodal lesion ≥ 15 mm in GTD.
 
Unequivocal progression of existing non-index lesions.
 
Bone marrow that was negative and is now positive.
 
Any new circulating lymphoma cells in blood cell count and/or pleural fluid.
 
Any new circulating blasts in the blood cell count.

Unable to Evaluate	
Incomplete data (ie, missing scans or unreadable images).
 
Not all non-index lesions evaluated.
 
Non-index lesions not assessed.

Not Applicable	No non-index lesions at baseline.

Overall Response

Index Lesions	Non-Index lesions	New Lesions	Overall Response
CR	CR	No	CR
CR	SD/IR	No	PR
CR	UE	No	CR
CR	NA	No	CR
PR	CR	No	PR
PR	SD/IR	No	PR
PR	UE	No	PR
PR	NA	No	PR
SD	CR	No	SD
SD	SD/IR	No	SD
SD	UE	No	SD
SD	NA	No	SD
RD/PD	Any	Yes/No	RD/PD
Any	RD/PD	Yes/No	RD/PD
Any	Any	Yes	RD/PD
UE	Non-PD	No	UE

- Adapted from: Cheson B, Pfistner B, Juweid M, et al. Revised Response for Malignant Lymphoma. *Journ Clin Onc.* 2007;25(5):579-586.

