- If CR determination depends on a residual lesion that decreased in size but did not disappear completely, it is recommended the residual lesion be investigated with biopsy or fine needle aspirate. If no disease is identified, objective status is CR.
- If progression determination depends on a lesion with an increase possibly due to necrosis, the lesion may be investigated with biopsy or fine needle aspirate to clarify status.

Subjective progression

Patients requiring discontinuation of treatment without objective evidence of disease progression should not be reported as PD on tumor assessment CRFs. This should be indicated on the end of treatment CRF as off treatment due to Global Deterioration of Health Status. Every effort should be made to document objective progression even after discontinuation of treatment.

Table 12. Objective Response Status at Each Evaluation

Target Lesions	Non-target Disease	New Lesions	Objective status
CR	CR	No	CR
CR	Non-CR/Non-PD	No	PR
CR	Indeterminate or Missing	No	PR
PR	Non-CR/Non-PD, Indeterminate, or Missing	No	PR
SD	Non-CR/Non-PD, Indeterminate, or Missing	No	Stable
Indeterminate or Missing	Non-PD	No	Indeterminate
PD	Any	Yes or No	PD
Any	PD	Yes or No	PD
Any	Any	Yes	PD

If the protocol allows enrollment of patients with only non-target disease, the following table will be used:

Table 13. Objective Response Status at Each Evaluation for Patients with Non Target Disease Only

Non-target Disease	New Lesions	Objective status
CR	No	CR
Non-CR/Non-PD	No	Non-CR/Non-PD
Indeterminate	No	Indeterminate
Unequivocal progression	Yes or No	PD
Any	Yes	PD

- Adapted from: Eisenhauer EA, Therasse P, Bogaerts J, et al. New response evaluation criteria in solid tumours: revised RECIST guideline (version 1.1). *Eur J Cancer*. 2009 Jan;45(2):228-47.

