ORR by treatment group will be calculated along with the 2-sided 95% CI using the Clopper-Pearson method (exact CI for a binomial proportion as computed by default by the FREQ procedure using the EXACT option).

In addition, the frequency (number and percentage) of patients with a BOR of CR, PR, SD, PD, and NE will be tabulated. Patients with BOR of NE will be summarized by reason for having NE status. The following reasons will be used:

- No baseline assessments.
- No post-baseline assessments due to death.
- No post-baseline assessments due to other reasons.
- All post-baseline assessments have overall response NE.
- New anti-cancer therapy started before first post-baseline assessment.
- SD of insufficient duration (<6 weeks after 'start date').
- PD too late (>12 weeks after 'start date').

Special and rare cases where BOR is NE due to both early SD and late PD will be classified as 'SD too early'.

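### The lymphoma response table scores index-lesion CR with unevaluable non-index lesions as overall CR, against its own CR definitions, so the tabulated CR rate can be overstated.

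*Protocol*

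**What the plan says.** Protocol Appendix 3 gives three layers of rules for NHL response.

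- **Index lesions.** CR is "Complete disappearance of all detectable clinical and radiographic evidence of disease", with nodes back to normal size and any enlarged liver or spleen normalised.
- **Non-index lesions.** CR is "Complete disappearance of all non-index lesions". UE covers incomplete data, and includes "Not all non-index lesions evaluated" and "Non-index lesions not assessed". A separate code, NA, is kept for patients with "No non-index lesions at baseline".
- **Overall Response table.** With index CR and no new lesion, the overall result is CR if non-index is CR, PR if non-index is SD/IR, CR if non-index is UE, and CR if non-index is NA.

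For solid tumours, Table 12 in Protocol Appendix 2 scores target CR with non-target disease "Indeterminate or Missing" and no new lesion as PR.

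SAP 6.2.2.1 derives BOR from the overall responses reported at each evaluation. For NHL, one CR before progression is enough for a BOR of CR. The section also states that a status of PR or SD cannot come after CR. Objective response is a BOR of CR or PR. Besides ORR, the number and percentage of "patients with a BOR of CR, PR, SD, PD, and NE will be tabulated".

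**The concern.** Disappearance of a lesion cannot be documented at a visit where the lesion was not assessed, yet the UE row awards CR at exactly that visit. The row cannot be meant for patients without non-index disease, because NA already covers them.

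Two consequences follow. First, an incomplete assessment is treated more favourably than a complete one that shows residual disease. Second, because one unconfirmed CR settles BOR for NHL, a single incomplete scan can place a patient in the CR row of the SAP table. What is at stake is the CR percentage, a planned output that readers will use to describe depth of response. The primary endpoint of the Portion B expansion cohorts is not at stake.

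**Working it through.** **Step 1. The index-CR rows side by side (no new lesion).**

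| Non-index status | What it means | Overall result |
|---|---|---|
| CR | all non-index lesions gone | CR |
| NA | none present at baseline | CR |
| SD/IR | at least one still present | PR |
| UE | present at baseline, clearance not shown | CR |

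The first three rows agree with the appendix's definitions. The fourth does not. It gives CR where neither the overall wording of the CR definition nor the non-index CR definition has been shown to be met. The CR definition is printed under the index-lesion heading, but its wording covers all disease, and the non-index definition alone produces the same conflict.

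**Step 2. Follow the row into the SAP.** Take a patient with non-index disease at baseline who is index CR / non-index UE at one visit and index CR / non-index SD/IR at the next. The table gives CR, then PR. BOR is CR under the one-visit rule, although the only informative assessment of the non-index lesions showed persistence. The sequence CR then PR is also one that SAP 6.2.2.1 says cannot occur. No rule in the SAP overrides the row.

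**Step 3. What changes if the cell becomes PR.**

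- ORR: CR and PR both count, so the change is 0.
- Duration of response and time to response (SAP 6.2.2.3 and 6.2.2.4): both use the first CR or PR, so the date is the same and the change is 0.
- BOR of CR: falls by one for each patient whose every CR visit is CR/UE. A patient with a fully assessed CR at any other visit before progression keeps a BOR of CR.

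**Step 4. Size per patient.** The only related figures in the plan are the FL precision figures in Protocol 9.3, and they reproduce. With Clopper-Pearson limits taken as the 0.025 quantile of Beta(x, n−x+1) and the 0.975 quantile of Beta(x+1, n−x):

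- 40/80: 38.6 to 61.4
- 44/80: 43.5 to 66.2
- 48/80: 48.4 to 70.8
- 56/80: 58.7 to 79.7
- maximum SE: √(0.25/80) = 0.0559, stated as 0.06

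None of these depends on the disputed row. The plan states no CR rate and no frequency of non-index UE.

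Using the protocol's FL sizes (80 at the selected dose in Section 9.3; up to 20 in each of FL-1 and FL-2 in Section 3.1.2), one affected patient shifts the CR rate by 1/80 = 1.25 points or 1/20 = 5 points. The SAP summarises by dose-level treatment group, so the actual denominators may differ; the shift is 1/n in any case.

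**Step 5. Illustration with assumed counts.** Assume 16/80 or 4/20 patients have a CR that does not rely on the row, and add k whose CR relies on it. The SAP plans a confidence interval for ORR only; the intervals here are for scale.

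| n | k | CR rate, % (95% CI) |
|---|---|---|
| 80 | 0 | 20.0 (11.9, 30.4) |
| 80 | 1 | 21.3 (12.9, 31.8) |
| 80 | 2 | 22.5 (13.9, 33.2) |
| 80 | 4 | 25.0 (16.0, 35.9) |
| 80 | 8 | 30.0 (20.3, 41.3) |
| 20 | 0 | 20.0 (5.7, 43.7) |
| 20 | 1 | 25.0 (8.7, 49.1) |
| 20 | 2 | 30.0 (11.9, 54.3) |

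**The case against.** **The effect is on a supplementary output.** This stands in part. In the expansion cohorts the efficacy endpoints are objective response, DR, TTR, PFS and OS, and the CR percentage is an added tabulation. SAP 3.2.2 does list BOR as an endpoint in dose escalation. A reader might go further and infer that the CR rate drives dose selection. The documents do not say so: Protocol 3.1.2 bases the FL-3 dose on an overall evaluation that includes tolerability, efficacy and PK, and Section 3.6 bases the RP2D on the primary and secondary endpoints.

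**Safeguards exist.** Marrow sampling is required for a potential CR (Protocol Table 5, footnote 32), clinical findings and laboratory results contribute to response, and FL images are collected for potential central review (footnote 22). These reduce the risk. None requires unassessed non-index lesions elsewhere to be examined before CR is assigned, and the central review is only a possibility.

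**Table 12 belongs to a different criteria set.** This stands. Appendix 2 adapts RECIST 1.1 and Appendix 3 adapts Cheson 2007, so a reader should not treat the difference as a contradiction in itself. It is supporting evidence only; the conflict inside Appendix 3 carries the point.

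**PR is not the only possible repair.** Every UE row in the table carries the index status forward, and the PR definition requires no growth of other nodes, liver or spleen, which an unassessed non-index node cannot show either. It is true that the text does not force PR over UE. PR is preferred because it agrees with the SD/IR row and leaves ORR alone. If the cell became UE, ORR would fall for any patient with no other CR or PR visit.

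**Conclusion.** The row conflicts with Appendix 3's own definitions of CR and can let missing data produce a better category than observed residual disease. Relative to PR it can only raise the CR count, and it can generate a CR-then-PR sequence that the SAP excludes. The size is 1.25 points of CR rate per affected patient at n=80 and 5 points at n=20. ORR, DR and TTR do not change if the cell becomes PR.

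How many patients would be affected is unknown. A reader might infer an overstatement of 1.5 to 6 points by assuming 24 index-lesion CRs among 80 patients, 5 to 20% of them with unevaluable non-index lesions (24 × 0.05/80 = 1.5 points; 24 × 0.20/80 = 6 points). The documents supply neither input. For those inputs the range is also an upper bound, because a fully assessed CR at another visit keeps the BOR of CR. The supported statement is that the CR rate can be overstated, not that it will be by a known amount. The point merits correction because it affects a reported result and is cheap to repair.

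**What to change.** In the Appendix 3 Overall Response table, change the result for index CR, non-index UE and no new lesion from CR to PR. Overall CR then requires every baseline non-index lesion to have been assessed and found gone, or no such lesion to have existed. State the same rule in the NHL part of SAP 6.2.2.1 and apply it when BOR is derived, so that a CR reported through this row does not set BOR. This also removes the CR-then-PR sequence that the row creates.

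The cost is one table cell, one sentence in the SAP and a derivation check. Enrolment, treatment and the primary ORR are untouched. The downside is that the reported CR rate may fall slightly.

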- Partial Response (PR): Greater than or equal to 30% decrease under baseline of the sum of diameters of all target measurable lesions. The short diameter is used in the sum for target nodes, while the longest diameter is used in the sum for all other target lesions. All target lesions must be assessed.
- Stable: Does not qualify for CR, PR or Progression. All target lesions must be assessed. Stable can follow PR only in the rare case that the sum increases by less than 20% from the nadir, but enough that a previously documented 30% decrease no longer holds.
- Objective Progression (PD): 20% increase in the sum of diameters of target measurable lesions above the smallest sum observed (over baseline if no decrease in the sum is observed during therapy), with a minimum absolute increase of 5 mm.
- Indeterminate. Progression has not been documented; and
 - One or more target measurable lesions have not been assessed;
or
 - Assessment methods used were inconsistent with those used at baseline;
or
 - One or more target lesions cannot be measured accurately (eg, poorly visible unless due to being too small to measure);
or
 - One or more target lesions were excised or irradiated and have not reappeared or increased.

Non-target disease

- CR: Disappearance of all non-target lesions and normalization of tumor marker levels. All lymph nodes must be 'normal' in size (<10 mm short axis).
- Non-CR/Non-PD: Persistence of any non-target lesions and/or tumor marker level above the normal limits.

- PD: Unequivocal progression of pre-existing lesions. Generally the overall tumor burden must increase sufficiently to merit discontinuation of therapy. In the presence of SD or PR in target disease, progression due to unequivocal increase in non-target disease should be rare.
- Indeterminate: Progression has not been determined and one or more non-target sites were not assessed or assessment methods were inconsistent with those used at baseline.

New Lesions

The appearance of any new unequivocal malignant lesion indicates PD. If a new lesion is equivocal, for example due to its small size, continued assessment will clarify the etiology. If repeat assessments confirm the lesion, then progression should be recorded on the date of the initial assessment. A lesion identified in an area not previously scanned will be considered a new lesion.

Supplemental Investigations

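### In Protocol Appendix 3 a scan showing only normal-sized nodes can meet both the CR and the PD definition, because PD by SPD rise has no size floor; DR and PFS in Portion B can then end on measurement variation

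*Protocol*

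**What the plan says.** Protocol Appendix 3 governs response in Portion B. In its table for index lesions, the PD row is a 50% or greater "increase in SPD of previously involved sites from nadir" and nothing more. The CR row requires that "All lymph nodes must have returned to normal size". A node whose GTD was 15 mm or more qualifies when "it must have returned to < 15 mm". The next sentence, which opens with the short axis, says "it must have returned to ≤ 10 mm".

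Size floors appear elsewhere. The non-index table counts as PD "Any new nodal lesion ≥ 15 mm in GTD", but only for new nodes. Appendix 2, for solid tumors, requires a 20% increase "with a minimum absolute increase of 5 mm".

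The Overall Response table in Appendix 3 can return CR when the index lesions are CR, and returns RD/PD whenever they are RD/PD. It does not say what to do when they are both.

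The SAP adds no floor. Section 6.2.2.1 repeats the 50%-from-nadir threshold for NHL and rules out PR or SD after a CR. Sections 6.2.2.3 and 6.2.2.5 end DR and PFS at the first documented PD or death, and no confirmation of PD is stated.

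**The concern.** A percentage rule taken from nadir becomes more sensitive as the nadir falls. With small residual nodes, a change of under 2 mm per diameter is enough for PD, yet the nodes may still be of a size the CR row accepts. After a CR, the SAP leaves no intermediate category to absorb such a change.

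DR and PFS in Portion B are at stake. An artificial PD shortens both, and the patients most exposed are those who responded best. It may be hard to undo, since footnote 22 to the expansion-cohort Schedule of Activities (Protocol Table 5) runs scans only until objective progression. Because the text supports either code, two investigators could also record the same scan differently.

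**Working it through.** The documents give no figure to reproduce, so the check is arithmetic on the definitions, followed by a simulation under stated assumptions.

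**Inputs from Appendix 3.** PD: SPD at least 1.5 x nadir SPD. CR node limits: GTD below 15 mm, short axis 10 mm or less. SPD: "sum of the product diameters (SPD) of the index lesions will be the baseline value used in determining response", from up to 6 index lesions, each the product of two perpendicular diameters.

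**Change needed per diameter.** sqrt(1.5) = 1.225, so 8 mm becomes 8 x 1.225 = 9.8 mm, a change of 1.8 mm.

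**Overlap, single node:**

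| Nadir (mm) | Later scan (mm) | SPD (mm²) | Change | Within CR limits? | PD? |
|---|---|---|---|---|---|
| 8x7 | 10x9 | 56 to 90 | +61% | yes | yes |
| 10x9 | 14x10 | 90 to 140 | +56% | yes | yes |
| 6x5 | 8x6 | 30 to 48 | +60% | yes | yes |
| 9x8 | 11x10 | 72 to 110 | +53% | yes | yes |

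Six nodes all going from 8x7 to 10x9 mm give the same +61%. The largest product within the CR limits is just under 15 x 10 = 150 mm², so any single-node nadir below 150/1.5 = 100 mm² leaves room for the overlap.

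**Effect on a recorded response.** Expansion eligibility (Protocol Section 4.1) asks for a nodal product of at least 2.25 cm² = 225 mm². If that node is the only index lesion, a nadir below 100 mm² is a fall of more than 1 - 100/225 = 56%, so the 50% PR threshold has already been passed. SAP Section 6.2.2.1 needs one CR or PR before progression and no confirmation in NHL. A later PD therefore does not remove the response.

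**Frequency.** Assumptions, none from the documents: true node size constant; independent normal error on each diameter; six scans (five 8-week intervals, 40 weeks); PD when SPD is at least 1.5 x the lowest earlier SPD. Proportion of patients with at least one false PD, nodes truly 8x7 mm, 100,000 patients per setting:

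| Error SD | 1 node | 2 nodes | 3 nodes | 6 nodes |
|---|---|---|---|---|
| 0.5 mm | 2% | 0% | 0% | 0% |
| 0.7 mm | 16% | 2% | 0.1% | 0% |
| 1.0 mm | 48% | 17% | 6% | 0.2% |
| 1.5 mm | 78% | 54% | 35% | 9% |

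**Effect of requiring an abnormal node on the PD scan** (both diameters above 10 mm; one node, SD 1.0 mm):

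| True size | Rule as written | With the size condition |
|---|---|---|
| 8x7 mm | 48% | 0.02% |
| 10x9 mm | 26% | 13% |
| 12x10 mm | about 15% | 14% to 15% |

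**The case against.** Four points can be made against this.

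*The frequency is assumed.* This stands. The documents give neither the measurement error nor the number and size of residual nodes. At an SD of 0.5 mm, or with six nodes at 1.0 mm, the problem is negligible. Appendix 3 says "conventional CT or MRI should be performed with contiguous slices of 10 mm or less in thickness", but it also sets 8 mm or less for spiral CT and asks for the same method throughout, so the 10 mm figure alone should not be read as the typical error.

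*A rule may exist elsewhere.* Appendix 3 is adapted from the Cheson 2007 criteria, which cannot be consulted here, and Protocol Section 7.7 (Tumor Response Assessment) is not visible in the public version. The claim is therefore limited to the absence of a visible precedence rule.

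*Responses are investigator-reported.* An investigator may well code such a scan as CR, so the rule can end DR and PFS; it does not always do so.

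*The endpoints are secondary and descriptive.* SAP Section 5.1.1 plans no hypothesis tests. This limits the consequence but leaves the contradiction in place.

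A reader might also infer that the two CR sentences conflict and so disturb the primary ORR: a node going from 16x12 to 14x11 mm passes the 15 mm limit but fails the 10 mm limit. The documents do not support this. The size sentences sit under a general requirement of normal size, and Appendix 3's section on measurable/abnormal lesions treats a node with GTD above 10 and up to 15 mm and perpendicular above 10 mm as abnormal. A 14x11 mm node is thus not normal. With SPD falling from 192 to 154 mm² (-20%), the status is SD on a reading of the whole appendix.

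**Conclusion.** The overlap between CR and PD is certain from the visible text of Appendix 3 and needs no assumption. Its consequence is confined to DR and PFS in Portion B, where a PD within measurement variation can end either. The exposed patients are deep responders with one or a few small residual nodes. No effect on the primary ORR is shown.

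The size is uncertain. For stable 8x7 mm nodes over six scans, false PD runs from 2% to 78% with one node and from 0% to 9% with six, as the assumed error SD goes from 0.5 to 1.5 mm. These are conditional rates for patients with such nodes and should not be applied to the whole cohort. The point merits a correction because a stated rule can give a wrong result and the repair is cheap.

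**What to change.** **Protocol Appendix 3, PD row.** Count the 50% SPD rise only if at least one previously involved lesion is abnormal on that scan by the appendix's own definition: for nodes, GTD above 10 mm and perpendicular above 10 mm; for nonnodal lesions, at least 10 mm in two perpendicular dimensions. With the CR limit of 10 mm read as the short axis, no node can then satisfy both rows.

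**CR row.** At most, state that the 10 mm limit applies to the short axis. Do not restrict the second sentence by baseline GTD: a 16x12 mm node shrinking to 14x11 mm would then pass the only numeric limit left, after a 20% SPD fall, and the overlap would return.

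**SAP Sections 6.2.2.3 and 6.2.2.5.** List every PD called while all index nodes are normal-sized, and add a DR and PFS sensitivity analysis that does not count those calls. Where scanning stopped at that PD, the patient would be censored there, so the listing should show how many have later scans.

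**Cost.** One condition in the PD row, one listing and one sensitivity analysis; Appendix 3 already has both diameters recorded. The condition removes nearly all false PD for 8x7 mm nodes at SD 1.0 mm, about half for 10x9 mm and almost none for 12x10 mm. A true relapse in small nodes may be dated one scan later. A long, narrow node (for example 18x9 mm) is too long for CR but not abnormal by the appendix's definition, so the amendment should say how it is coded.
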